cortical/cancellous allograft in conjunction with an approved Depuy Synthes pedicle screw system compared to autograft mixed with cortical/cancellous allograft in conjunction with the same DePuy Synthes pedicle screw system used for a one or two- level posterolateral lumbar fusion.

Methodology

Study Design

This is a prospective randomized, non-blinded, controlled study. Patients with a diagnosis of degenerative disc disease and/or up to grade I spondylolisthesis and planning to undergo a 1- or 2-level instrumented posterolateral lumbar fusion surgery between L1-S1 will be screened. If eligible and the subject meets all the inclusion criteria and none of the exclusion criteria, the subject will be approached about study participation by the surgeon. If the subject agrees to participate, the consent process will be initiated by the study coordinator. Once the patient has been consented; data including medical history, neurological exam, patient questionnaires (VAS, ODI, SF-36) will be collected. Randomization will occur once a surgery date has been scheduled so the appropriate instrumentation can be boarded accordingly. A randomization envelope will reveal randomization treatment group. The envelopes will be generated in a 1:1 fashion and be randomly allocated to an assigned study identification number. Subjects will be randomized to either: 1) treatment arm where the investigator will use an FDA approved/cleared DePuy Synthes spinal pedicle screw system with ViviGen® Cellular Bone Matrix mixed with cortical/cancellous allograft or the 2) control arm where the investigator use the same DePuy Synthes spinal pedicle screw system with local autologous bone graft mixed with cortical/cancellous allograft. Both treatment groups represent standard of care lumbar fusion surgeries using two types of bone graft options to create the arthrodesis as comparators.

Once the lumbar fusion surgery has taken place as planned; data will be collected regarding the surgery performed, including operative time, amount of bone graft used, spinal system used, length of hospital stay, and adverse events/complications.

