Study subjects will be followed up at 6-weeks, 3-months, 6-months, and 12-months postoperatively at the private practice or clinic. During these routine (standard of care) postoperative visits, subjects will complete questionnaires (VAS, ODI, SF-36, patient satisfaction) and have neurological exam (lumbar spine exam, see appendix 1) completed by the investigator. Adverse events related to device and/or procedure will be evaluated as each postoperative visit. AP and lateral x-rays will be performed at all visits with flexion and extension x-rays added at baseline, 3-months, 6-months, and 12-months. A CT scan of the lumbar spine will be performed during the 12-month postoperative time frame at the Beaumont-RO Imaging Center. Radiographic analysis will be performed and evaluated for fusion status as evidenced by bony bridging, presence of radiolucency, and development of pseudoarthrosis at each follow-up visit.

This study design reflects the current standard of care for lumbar spinal stenosis, degenerative disc disease and lumbar degenerative spondylolisthesis. Lumbar fusion surgery using pedicle screw fixation with autograft and allograft bone grafting options is treatment of choice after conservative (non-surgical) therapies have been implemented and failed.

Statistical Analysis

The sample size will consist of 40 patients; 20 in each treatment arm. The primary hypothesis is that the probability of achieving fusion using ViviGen bone graft is not clinically inferior to using autograft and allograft in lumbar fusion at 12-months post-surgery. Using a one-sided test and fusion rate of 86%, there is a 0.80 probability of 0.80 of finding a difference for 60 patients. A 10% dropout rate was considered. Forty patients may result in low statistical power; however, this may be increased by 10 in each arm once enrollment has obtained and if needed, and upon agreement with study sponsor. Enrollment of 40 reflects the current allotted grant/budget per the study sponsor for this project.

There are other studies that analyzed demineralized bone matrix in two-year fusion outcomes for lumbar spinal fusions that used a similar size population (range between 13 and 28 patients) to the proposed enrollment for this study, as demonstrated in *Vaccaro et al (2007)* and *Kang et al (2012)*. Power calculation for the primary outcome of bone fusion was obtained using PASS 15. An 86% fusion rate (Kang et al) was assumed with a 10% dropout rate for both arms.

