Secondary endpoints (VAS, ODI, SF-36, neurological status, and fusion) will be quantified to detect changes longitudinally from baseline through 12-months post-surgery.

Study Population and Inclusion/Exclusion Criteria

Patients with a diagnosis of spinal stenosis, degenerative disc disease and/or up to grade I spondylolisthesis and planning to undergo a 1 or 2-level instrumented posterolateral lumbar fusion surgery between L1-S1 will be asked to participate in the study. If eligible, the consent process will be initiated by the study coordinator

A subject may be included if the following criteria are met:

1. ≥ 18 years of age
2. Able to provide consent
3. Is undergoing standard of care one or two-level instrumented posterolateral fusion at the level between L1-S1
4. Has diagnosis of spinal stenosis, degenerative disc disease and/or up to Grade 1 spondylolisthesis
5. Requires decompression at intended fusion level (multi-level decompression allowed L1-S1)
6. Has failed 6-weeks or more of conservative, non-operative treatment
7. Has back and/or radicular lumbar symptoms with ODI (Oswestry Disability Index) score of ≥ 30 preoperatively.

A subject will be excluded if any of the following criteria are met:

1. Any prior lumbar fusion surgery
2. Requires fusion of more than two levels
3. Requires an interbody fusion based on relevant diagnosis and factors (such as foraminal stenosis, degree of spondylolisthesis, spinal deformity, disc space collapse, and subject's age) as determined by investigator
4. BMI > 40

5. Active systemic infection or infection at operative site
6. History of an osteoporotic fracture and/or vertebral body fracture
7. Is currently being treated with chemotherapy, radiation, immunosuppression or chronic steroid therapy
8. History of osteoporosis, osteopenia, or osteomalacia that would contraindicate spinal surgery
9. Psychological or physical condition in the opinion of the investigator that would interfere with subject self-assessments
10. History of neurological condition in the opinion of the investigator that may affect lumbar function and pain assessments
11. Subjects with a history of cancer must be disease free for at least 3 years
12. Pregnant, or plans on becoming pregnant

Intervention

Treatment arm/group: 20 subjects undergoing open, one or two-level instrumented posterolateral lumbar fusion surgery using ViviGen Cellular Bone Matrix mixed with cortical/cancellous allograft and DePuy Synthes pedicle screw system.

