Control arm/group: 20 subjects undergoing open, one or two-level posterolateral lumbar fusion surgery using local autograft mixed with cortical/cancellous allograft and DePuy Synthes pedicle screw system.

Data and Safety Monitoring

The PI and study team (including sub-investigators, clinical research manager) will be responsible for data and safety monitoring. All adverse events will be reviewed to determine relatedness to the product and reported to sponsor as necessary (if related to product and unanticipated according to risk profile). The data will be reviewed for maintenance of confidentiality and integrity as well as the data collection process. The data and safety review will take place every six months from the date of the first patient enrolled into the study or after every ten patients enrolled whichever comes first.

Adverse Events

Relevant adverse events (those related to the study device, the surgical procedure, or the lumbar spine) will be recorded in this study. All adverse events will be reviewed for relatedness and expectedness by the PI on a case by case basis and per Data and Safety Monitoring guidelines.

Protocol Deviations

The investigators are responsible for documenting all protocol deviations, including an explanation for why the deviation occurred. All protocol deviations will be recorded and submitted to the IRB per policy.

Outcomes

Primary Endpoint

IRB NUMBER: 2018-158

IRB APPROVAL DATE: 10/18/2019

- Successful lumbar fusion as measured by CT scan and flexion/extension x-rays at 12-months; as evidenced by bony bridging, presence of radiolucency, no development of pseudoarthrosis

Secondary Endpoints

- Improvement in patient reported outcomes as measured by VAS (\geq 2-point improvement), ODI (\geq 15-point improvement), SF-36 (\geq 15-point improvement) from baseline to 12-months.
- No new or worsening neurological (motor and sensory) deficit as compared to baseline through 12-months. No revision surgery and/or development of pseudoarthrosis by month 12.
- No occurrence of adverse events related to device by month 12.

Subject Screening and Enrollment

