| Study Objectives | 
 • Primary Objective: 
 1. To evaluate bone fusion using ViviGen Cellular Bone Matrix for one or two-level instrumented posterolateral lumbar fusion surgery • Secondary Objectives: 
 1. To evaluate VAS, ODI, SF-36 and patient satisfaction scores postoperatively compared to baseline/preoperative. 2. Evaluate the occurrence of procedure and/or device related adverse events |

| | |
|--------------------|--|
| Study Endpoints | 
Primary Endpoint:
 
 Successful lumbar bone fusion as measured by CT scan and flexion/extension x-rays at 12-months; as evidenced by bony bridging, presence of radiolucency, no development of pseudoarthrosis 
Secondary Endpoints:
 
 Improvement in patient reported outcomes as measured by VAS (\geq 2-point improvement), ODI (\geq 15-point improvement), SF-36 (\geq 15 point improvement) from baseline to 12-months. No new or worsening neurological (motor and sensory) deficit as compared to baseline through 12-months. No revision surgery and/or development of pseudoarthrosis by month 12. No occurrence of adverse events related to device by month 12. |
| Inclusion Criteria | 
A subject may be included if the following criteria are met:
 
 1. \geq18 years of age 2. Able to provide consent 3. Is undergoing standard of care one or two-level instrumented posterolateral fusion at the level between L1-S1 4. Has diagnosis of spinal stenosis, degenerative disc disease and/or up to Grade 1 spondylolisthesis 5. Requires decompression at intended fusion level (multi-level decompression allowed L1-S1) 6. Has failed 6-weeks or more of conservative, non-operative treatment 7. Has back and/or radicular lumbar symptoms with ODI (Oswestry Disability Index) score of \geq 30 preoperatively. |

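### The pain, function and SF-36 endpoints are defined only as 12-month responder thresholds, and no between-arm analysis of the scores is specified; a responder comparison at 18-20 per arm would lose information already collected

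*Combined protocol and SAP*

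**What the plan says.** All references are to the combined protocol and SAP.

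- **Endpoint definition.** Outcomes, Secondary Endpoints, and the Study Endpoints row of the synopsis give "Improvement in patient reported outcomes as measured by VAS" with a cut of at least 2 points, and cuts of at least 15 points for ODI and SF-36. The time frame is fixed: "15-point improvement) from baseline to 12-months". No mean, mean change or other continuous endpoint is listed.
- **Analysis.** The last sentence of the Statistical Analysis section is the only analysis statement for these measures: "Secondary endpoints (VAS, ODI, SF-36, neurological status, and fusion) will be quantified to detect changes longitudinally from baseline through 12-months post-surgery".
- **Objectives.** The Objective section sets out a randomized comparison of fusion rates and patient-reported outcomes, including pain and function, between the two graft arms. The secondary objective in the synopsis is a within-patient one: "To evaluate VAS, ODI, SF-36 and patient satisfaction scores postoperatively compared to baseline/preoperative".
- **Data and size.** "Study subjects will be followed up at 6-weeks, 3-months, 6-months, and 12-months postoperatively", with VAS, ODI and SF-36 completed at baseline and at each of those visits. "The sample size will consist of 40 patients; 20 in each treatment arm". A 10% dropout rate is assumed.

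**The concern.** A threshold rule treats a 14-point fall in ODI like no change, and a 15-point fall like a 40-point one. As written, the endpoint uses only the baseline and month-12 scores. A patient who misses month 12 has no endpoint value, even with scores at 6 weeks, 3 months and 6 months, and no rule covers that case.

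The sentence on longitudinal quantification does not fill the gap. It does not say what is compared between arms, by which model, or whether the baseline score enters as a covariate. An analyst who follows the endpoint definitions would tabulate responder percentages by arm. With 18-20 patients per arm, that uses the collected scores poorly for a comparison that the Objective asks for.

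**Working it through.** **The plan's own figure.** The only power statement (0.80 with 60 patients, one-sided, 86% fusion) concerns the primary fusion endpoint. It cannot be rebuilt, because neither the non-inferiority margin nor the alpha level is given, and it says nothing about VAS, ODI or SF-36. For these the documents give no SD, correlation, expected effect, responder rate or power.

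**Inputs from the documents.** 20 per arm, allocated 1:1; 10% dropout, so 20 × 0.9 = 18 evaluable per arm.

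**Assumed inputs.** Normally distributed scores with equal SD at baseline and month 12; baseline-to-month-12 correlation ρ = 0.3-0.7; true between-arm difference d = 0.5-1.0 SD; control responder rate p_c = 50-80%; two-sided 5% test.

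**Formulas** (n per arm)
- Treated responder rate: p_t = Φ(z(p_c) + d/√(2(1−ρ))).
- Responder power: Φ((|p_t − p_c| − 1.96·se₀)/se₁), where se₀ is the pooled and se₁ the unpooled standard error.
- Change-score t-test: standardized effect d/√(2(1−ρ)), noncentral t on 2n−2 df.
- Baseline-adjusted mean (ANCOVA): standardized effect d/√(1−ρ²), same df.

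**One case in full** (n = 20, ρ = 0.5, d = 0.8, p_c = 0.60)
- p_t = Φ(0.253 + 0.8) = 0.854.
- The pooled rate is 0.727, so se₀ = √(0.727 × 0.273 × 2/20) = 0.141.
- se₁ = √((0.60 × 0.40 + 0.854 × 0.146)/20) = 0.135.
- Responder power = Φ((0.254 − 1.96 × 0.141)/0.135) = 0.44.
- Change score: effect 0.8/1 = 0.8, power 0.69.
- ANCOVA: effect 0.8/0.866 = 0.924, power 0.81.
- Retained power: 0.435/0.812 = 54%.

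**Mid-range results** (ρ = 0.5, d = 0.8)

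| n per arm | Responder, p_c 60% | Responder, p_c 70% | Change score | ANCOVA | Retained against ANCOVA |
|---|---|---|---|---|---|
| 18 | 0.40 | 0.34 | 0.65 | 0.77 | 44-52% |
| 20 | 0.44 | 0.37 | 0.69 | 0.81 | 46-54% |

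**Whole grid.** Retained power runs from 32% (n = 18, ρ = 0.3, d = 0.8, p_c = 80%: 0.219 against 0.686) to 83% (n = 20, ρ = 0.7, d = 1.0, p_c = 50%: 0.817 against 0.991). With Fisher's exact test for the responders, it runs from 15% to 75%.

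**Where the loss comes from.** In the case worked above the total loss is 0.812 − 0.435 = 0.377. The cut-off accounts for 0.693 − 0.435 = 0.258 (68%), and the missing covariate for 0.812 − 0.693 = 0.119 (32%). The cut-off is the larger part in 64 of the 72 grid combinations. The 8 exceptions all have ρ = 0.3, where the cut-off's share is 41-49%.

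**On the ODI scale.** Simulated at 18 per arm, assuming SD 18, baseline at least 30, mean control improvement about 20 and ρ = 0.3-0.5:

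| True difference | Responder rule | Change score | ANCOVA |
|---|---|---|---|
| 5 points | 9-10% | not run | 14-15% |
| 10 points | 18-22% | 32-41% | 38-46% |
| 15 points | 34-43% | 61-73% | 72-78% |

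These figures are for ANCOVA at month 12. The repeated-measures model proposed below was not simulated separately.

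**The case against.** The strongest reply is that the plan never says the scores will be thrown away. The Statistical Analysis sentence promises longitudinal quantification, and the synopsis objective is to evaluate the scores themselves against baseline. A reader might infer from the threshold bullets that the plan has chosen to discard the continuous data; the documents do not support that. They leave two statements unreconciled and a method unstated. This part of the reply stands.

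A reader might also infer that baseline is ignored. It is not: each threshold is a change from the patient's own baseline. What is absent is baseline as a covariate.

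No between-arm test, alpha or power is stated for any patient-reported endpoint, so the loss arises only if the arms are compared on responder proportions. That is correct, but the Objective calls for a comparison of pain and function, and the only endpoints defined for it are the thresholds.

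The assumed effects are also large for two arms that the protocol calls standard of care. A 15-point between-arm ODI difference equals the plan's whole individual-response threshold. At 5 points neither method is useful, and at 10 points the adjusted mean still has less than 50% power. Changing the analysis therefore does not make the trial adequately powered for these endpoints.

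Finally, responder thresholds are a legitimate way to express clinical benefit. That supports reporting them; it does not support making them the only defined form of the endpoint at this sample size.

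**Conclusion.** The point holds as a gap in specification with a measurable cost. VAS, ODI and SF-36 are defined only as 2/15/15-point responders at 12 months, the longitudinal statement is not tied to those definitions, and no between-arm estimate, model or baseline covariate is given.

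If the arms are compared on responder proportions at 18-20 per arm, the comparison keeps about one third to four fifths of the power of a baseline-adjusted comparison of means, and roughly half at mid-range values. At those values most of the loss comes from the cut-off and a smaller part from not using baseline as a covariate; at correlation 0.3 the two parts can be similar. A flat statement that the plan loses half its power would go too far, because every input except the sample size and dropout is assumed.

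These are secondary endpoints, and power for modest differences stays low either way. The change is still worth making, because it needs only data that the trial already collects.

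**What to change.** In the Statistical Analysis section, the Secondary Endpoints list and the synopsis:

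1. Define the main analysis of each score as the between-arm difference in mean at month 12, with a 95% CI.
2. Estimate it from one repeated-measures model on the 6-week, 3-, 6- and 12-month scores, with the baseline score as covariate. Patients who miss month 12 then still contribute their earlier visits.
3. Name the VAS analysed (for example back or leg pain) and the SF-36 score analysed; the documents identify neither, and the model cannot be run without them.
4. Keep the 2/15/15-point responder percentages by arm as descriptive supporting results.

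The cost is protocol and SAP wording. No new data, visits or patients are needed. The downside is that the responder percentages become supportive.

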Bone graft substitute (BGS) materials offer an alternative to autograft bone capable of supporting new bone growth, while avoiding or minimizing the frequent co-morbidities associated with autograft harvest from the iliac crest.³⁻⁵ Allograft bone has been used successfully for more than two decades as a first-generation alternative to autograft bone. While traditional processed allograft bone can be difficult to shape, shows variable resorption characteristics, and variable biological activity, ViviGen® Cellular Bone Matrix has addressed these issues in their product. While containing all the properties required for bone formation, it additionally has a consistency that allows it to hold shape in a putty-like consistency.⁶ ViviGen® Cellular Bone Matrix can be molded into a specific form that allows proper placement, positioning and formation during posterolateral lumbar fusion.⁶

Description of ViviGen®⁶

ViviGen® is manufactured by DePuy Synthes, Inc. (West Chester, Pennsylvania). ViviGen® Cellular Bone Matrix is comprised of cryopreserved viable cortical cancellous bone matrix and demineralized bone. ViviGen® Cellular Bone Matrix is a Human Cells, Tissues, and Cellular and Tissue-based Product (HCT/P) as defined by the U.S. Food and Drug Administration in 21 CFR 1271.3. ViviGen® Cellular Bone Matrix is processed from donated human tissue, resulting from the generous gift of an individual or his/her family.

ViviGen® Cellular Bone Matrix contains all of the properties required for bone formation being that it is osteoconductive, osteoinductive and osteogenic. Safety of ViviGen® Cellular Bone Matrix is defined by every lot is aseptically processed and final product is tested for sterility using USP standards. Packaging and handling is beneficial in that all four sizes of ViviGen® Cellular Bone Matrix will thaw in less than 5 minutes, which is vital for cell viability, in that the ported pouch allows for the quick and efficient removal of the cryopreservation media and rinsing solutions. ViviGen® Cellular Bone Matrix maximizes cell viability by modes of processing that is focused on protecting viable lineage committed bone cells from recovery to implantation.

Objective

The objective of this study is to perform a prospective, randomized, controlled clinical trial to compare radiographic fusion rates and patient reported outcomes, including pain and function preoperatively and postoperatively, using Depuy ViviGen® Cellular Bone Matrix mixed with

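### The only adverse-event endpoint is limited to events related to an undefined 'device', so it is narrower than the safety objective, which also covers procedure-related events

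*Combined protocol and SAP*

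**What the plan says.** The plan describes adverse events in five places, and the scope differs.

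- **Endpoint** (Outcomes, Secondary Endpoints; repeated under Study Endpoints in the synopsis): "No occurrence of adverse events related to device by month 12".
- **Objective** (Study Synopsis, secondary objective 2): "Evaluate the occurrence of procedure and/or device related adverse events".
- **Visit assessment** (Methodology, Study Design): "Adverse events related to device and/or procedure will be evaluated as each postoperative visit".
- **Recording** (Adverse Events): "Relevant adverse events (those related to the study device, the surgical procedure, or the lumbar spine) will be recorded in this study".
- **Review** (Data and Safety Monitoring): "All adverse events will be reviewed to determine relatedness to the product".

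The Intervention section describes the treatment arm as "using ViviGen Cellular Bone Matrix mixed with cortical/cancellous allograft and DePuy Synthes pedicle screw system" and the control arm as "using local autograft mixed with cortical/cancellous allograft and DePuy Synthes pedicle screw system". Study Design says that the screw system is the same in both arms and that the study is not blinded. The Description of ViviGen section classes it as a human tissue product (HCT/P). The Adverse Events section has the principal investigator judge relatedness case by case.

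**The concern.** An endpoint should be able to answer its objective. Here the objective covers events from the procedure, the device or both, while the endpoint covers the device only. A patient with a procedure-related complication and no device-related event meets the endpoint as a success.

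The endpoint also turns on a word that the plan never defines. The arms differ in graft and share the screws, so what 'device' includes decides whether a control patient can have an event and whether a graft problem counts. Without a definition, that choice could be made after the data are seen, by staff who know the arm. The Introduction names clinical safety as a subject of the study, so the reported safety rate should not depend on such a choice.

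**Working it through.** The documents give no rate, power or sample size for this endpoint, so there is no figure to reproduce. The check is a comparison of texts.

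**Step 1: scope.**

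| Source | Device | Procedure | Lumbar spine |
|---|---|---|---|
| Endpoint (Outcomes and synopsis) | yes | no | no |
| Secondary objective 2 | yes | yes | not named |
| Visit assessment | yes | yes | not named |
| Recording rule | yes | yes | yes |

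The endpoint is the narrowest of the four. This holds for any meaning of 'device'.

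**Step 2: terms.** The plan uses 'device', 'study device' and 'product' and defines none of them. Classing ViviGen as a tissue product does not settle how the protocol uses 'device'. The sentence on relatedness to the product goes on to deal with reporting to the sponsor, so it does not define the endpoint either.

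**Step 3: the readings, given what each arm receives.**

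| 'Device' means | ViviGen arm | Control arm | Consequence |
|---|---|---|---|
| ViviGen alone | graft events count | no event possible, 0 of 20 by construction | no comparator |
| Screws alone | screw events count | screw events count | same rule in both arms, but graft events are missed |
| ViviGen and screws | graft and screw events count | screw events count; local autograft is not naturally a device | graft events may count in one arm only |

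No reading clearly applies one rule to both arms and also covers the graft, which is what was randomised.

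**Step 4: how far the definition moves the number.** This is an illustration with assumed rates, none of them from the documents. Let procedure or hardware events occur in 5% to 20% of each arm and ViviGen-specific events in 2% to 5% of the treatment arm, independently, with no autograft- or allograft-specific events.

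- ViviGen-only reading: treatment 2% to 5%, control 0%.
- Procedure and device both counted: treatment 1 − (1 − 0.05)(1 − 0.02) = 6.9% at the low end and 1 − (1 − 0.20)(1 − 0.05) = 24% at the high end; control 5% and 20%.

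The level in each arm changes a good deal. The difference between arms changes little: 6.9 − 5 = 1.9 points against 2, and 24 − 20 = 4 points against 5. So the wider endpoint restores the missing part of the objective. It does not sharpen a graft-specific signal, which is why a separate listing is needed.

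**The case against.** The strongest reply is that this is a wording mismatch with little consequence. Objective 2 asks only to evaluate occurrence. The comparative aim in the Objective section names fusion and patient-reported outcomes, not adverse events. The Statistical Analysis section leaves adverse events out of the secondary endpoints that it lists for longitudinal analysis, and no between-arm safety test is stated. Procedure-related events are recorded in both arms, and new or worsening neurological deficit, revision surgery and pseudoarthrosis are endpoints that apply equally to both. All of that stands, and it limits the harm. It does not remove the mismatch, because those endpoints do not cover every procedure- or graft-related event.

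A reader might infer something stronger: that the arms are not compared like with like, or that the control rate must be zero. The documents do not support that as a general statement. The structural zero needs 'device' to mean ViviGen alone. Both arms receive the same screws, so under either other reading control patients can have events. A reader might also put a number on the patients missed. Any such number would rest on assumed rates, and some of those patients may already be counted under revision, pseudoarthrosis or neurological deficit.

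It is also fair to say that a wider endpoint still depends on an unblinded judgement of relatedness. It reduces that dependence, since an event counts whichever of procedure, instrumentation or graft is named as the cause, but it does not end it.

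**Conclusion.** The concern holds in a limited form. The adverse-event endpoint is narrower than secondary objective 2 and than the events the trial assesses and records. That rests on the texts alone and needs no assumption. In addition, 'device', 'study device' and 'product' are undefined, and each plausible reading leaves the control arm without possible events, leaves out the graft, or may count graft events in one arm only. Which of these applies cannot be told from the documents.

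No magnitude can be stated, because the documents give no adverse-event rates. The point does not touch the primary fusion endpoint. It is worth correcting because safety is a stated purpose and the correction is cheap.

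**What to change.** In Outcomes and in the synopsis, restate the endpoint as: *no adverse event related to the procedure, the instrumentation or the graft material (ViviGen, autograft or allograft) by month 12*. Report it by arm under the same definition. List ViviGen-related events separately and descriptively for the treatment arm. Define 'device', 'study device' and 'product' once and use them consistently.

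The cost is one sentence in two places and a short definition, with no new patients or visits. The recording rule already covers device, procedure and lumbar-spine events, but it does not name autograft or allograft as a cause, so the adverse-event form may need that category. Event-free rates will look somewhat less favourable. Pooling graft events with procedure events can dilute a graft-specific signal with 20 patients per arm, hence the separate listing. Relatedness will still be judged by an investigator who knows the arm.
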